7.11 Management of Cetuximab Hypersensitivity Reactions

CTCAE Grade	Hypersensitivity Reaction
Grade 1	Transient flushing or rash, drug fever <38°C (<100.4°F); intervention not indicated
Grade 2	Intervention or infusion interruption indicated; responds promptly to symptomatic treatment (e.g., antihistamines, NSAIDS, narcotics); prophylactic medications indicated for <=24 hrs
Grade 3	Prolonged (e.g., not rapidly responsive to symptomatic medication and/or brief interruption of infusion); recurrence of symptoms following initial improvement; hospitalization indicated for clinical sequelae (e.g., renal impairment, pulmonary infiltrates)
Grade 4	Life-threatening consequences; urgent intervention indicated

^a Symptoms of hypersensitivity reactions should be managed per institutional chemotherapy infusion policy guidelines.

^b Study Therapy Retreatment Following Hypersensitivity Reactions: Once a cetuximab infusion rate has been decreased due to an allergic/hypersensitivity reaction, it will remain decreased for all subsequent infusions. If the subject has a second allergic/hypersensitivity reaction with the slower infusion rate, the infusion should be stopped, and the subject should receive no further cetuximab treatment. If a subject experiences a Grade 3 or 4 allergic/hypersensitivity reaction at any time, the subject should receive no further cetuximab treatment. If there is any question as to whether an observed reaction is an allergic/hypersensitivity reaction of Grades 1-4, the Principal Investigator should be contacted immediately to discuss and grade the reaction.

7.12 Cetuximab Special Instructions

If cetuximab is omitted for more than four consecutive infusions for toxicity due to cetuximab, or for an intercurrent illness (e.g., infection) requiring interruption of therapy, the subject should be discontinued from further cetuximab therapy. If toxicities prevent the administration of cetuximab, the subject may continue to receive radiation therapy.

7.13 Retreatment Criteria for cetuximab

7.13.1 Cetuximab may only be administered if all of the following criteria are met regardless of cycle, providing no criteria for discontinuation are met (see Section 13.0).

7.13.2 Acne-like rash is \leq Grade 2 (see Section 7.14)

[figure not shown]
7.13.3 Grade 3 - 4 hematologic toxicities have resolved to \leq CTC Grade 2

7.13.4 Grade 3 - 4 non-hematologic toxicities have resolved to \leq CTC Grade 2,
(except fatigue (asthenia), anorexia and alopecia)

7.14 Acne-Like Rash (rash maculo-papular)

The dose of cetuximab will be adjusted for Grade 3 acne-like rash. The severity of these events will be graded according to the criteria for the CTC term "rash maculo-papular." The cetuximab dose alteration scheme is outlined in the figure below. If a subject experiences a Grade 3 acne-like rash, cetuximab therapy is to be held for up to four consecutive infusions (see table below). The Investigator could also consider concomitant treatment with topical and/or oral antibiotics and topical corticosteroids. If there are subsequent occurrences of a Grade 3 acne-like rash, cetuximab therapy may again be omitted for up to four consecutive weeks. Treatment may resume with reduced doses of cetuximab if the skin toxicity has resolved to Grade 2 or less. Cetuximab dose reductions are permanent. Cetuximab will be discontinued if there is a subsequent occurrence of a fourth episode of Grade 3 acne-like rash or there are more than four consecutive infusions held. The subject should be followed weekly until resolution of the rash. If a subject experiences a Grade 4 acne-like rash, cetuximab therapy will be discontinued.

Management of Cetuximab Acne-Like Rash

8.0 RADIOTHERAPY

- 8.1 Immobilization, imaging and target definitions
 - 8.1.1 The technical details of RT planning will correspond to standard of care at the Department of Radiation Oncology as previously published (29).
 - 8.1.2 Target doses will be similar to the doses delivered in standard practice: 70 Gy at 2.0 Gy/fraction to primary tumor and to lymph nodes with clinical/radiological evidence of metastases, and 56-63 Gy at 1.6-1.8 Gy/fraction to subclinical disease around the primary tumor or to the surgical tumor excision bed, and to the lymph nodes at risk of metastasis, all in 35 fractions, over 7 weeks.
- 8.2 Optimization goals regarding the salivary glands will be:
 - 8.2.1 Mean dose to the parotid glands <26 Gy (at least one gland).
 - 8.2.2 The dose to the volumes of the submandibular glands and oral cavity outside the targets will be minimized.
 - 8.2.3 The doses to the swallowing structures (pharyngeal constrictors, glottic and supraglottic larynx) outside the targets will be minimized, aiming at mean dose < 50 Gy.
- 8.3 OPTIMIZATION CONSTRAINTS WILL BE:
 - 8.3.1 The maximal target PTV dose will be 110% of the prescribed dose.
 - 8.3.2 The minimum target PTV doses will be > 99% of the prescribed dose.
 - 8.3.3 The maximal dose outside the targets will be <105% of the prescribed dose delivered to at least 0.5 cc. volume.
 - 8.3.4 The maximal dose to the spinal cord, expanded 0.5 cm, will be < 50 Gy, to the non-expanded cord < 45 Gy, to the optic pathways < 50 Gy and to the brainstem <54 Gy.

9.0 EVALUATION OF RESPONSE TO TREATMENT

- 9.1 Evaluation of tumor extent will be recorded for the primary tumor and regional nodes at each f/u interval. PET-CT scans will be performed 12-14 weeks (+/- 1 month) after the completion of therapy to assess response.
- 9.2 Patients with any nodes who are PET-CT positive at 12-14 weeks (+/- 1 month) post cetuximab-RT may be considered for neck dissection. Patients with palpable residual nodes at 3 months whose PET-CT shows a complete response (CR) may undergo clinical observation and periodic PET scans according to the judgment of the treating clinicians.
- 9.3 Clinical examinations will be performed as comparable to clinical practice: at 1 month after the completion of therapy and then every 2 months during years 1 and 2, and at 3-month intervals during year 3, after which follow-up will be performed according to clinical practice. Allowable windows for these exams are +/- 1 month.

Clinical examinations will be performed by medical oncology, radiation oncology, and/or surgical oncology. To meet the examination requirements, patients need to be seen by at least one discipline (but not all three) during the aforementioned time intervals.

9.4 Once patients discontinue treatment (Section 13.0) or have tumor progression/recurrence, they will be followed as clinically indicated for 3 years following the completion of radiation and/or cetuximab.

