11.0 STUDY CALENDAR

Assessment	Pre-Treatment*	Day 0 Loading Dose	Day 7 (+/- 2 days)	Weekly during Treatment†	12-14 wks post RT (+/- 1 month)	Follow Up ³
H&P/Physician Evaluation	X			X	X	X
Smoking status and tumor HPV or p16 determination	X					
Biopsy	X		X ¹			
Buccal swab	X		X ¹			
COMP, Mg	X			X	X	
CBCP with diff	X			X	X	
PET-CT	X				X ²	
Dental Evaluation	X					
Toxicity Evaluation	X			X	X	X
QOL Questionnaire	X				X	X
Videofluoroscopy	X				X	X
Cetuximab		X		X		

* The pre-treatment period is prior to the administration of the cetuximab loading dose

† Radiation therapy will start within 4 days following Day 7 biopsy

¹Research biopsy will be performed 7 days (+/- 2 days) after cetuximab. This second biopsy will only be obtained if it can be done without general anesthesia.

²Restaging PET-CT will be obtained at 12-14 weeks.

³Follow Up: Examinations will be performed as comparable to clinical practice: at 1 month after the completion of therapy and then every 2 months during years 1 and 2, and at 3-month intervals during year 3. Toxicity evaluation will be collected at each visit. Quality of Life Questionnaires will be given to patients at follow-up visits 1, 3, 6, 12, 18, 24 and 36 months. Videofluoroscopy will be performed at 3, 12, and 24 months after therapy. Allowable windows for all these time points are +/- 1 month.

Note: Once patients discontinue treatment (Section 13.0) or have tumor progression/recurrence, they will be followed as clinically indicated for 3 years following the completion of radiation and/or cetuximab.

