13.0 CRITERIA FOR DISCONTINUATION OF TREATMENT

Unacceptable adverse event(s), intercurrent illness which prevents further administration of treatment, patient preference, progressive disease, life threatening or other unacceptable drug-related toxicity, changes in the patient's condition that render the patient unacceptable for

further treatment in the judgment of the investigators.

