20.0 STATISTICAL CONSIDERATIONS

20.1 Study Design

This is a Phase II trial of seven weeks RT+cetuximab for head and neck cancer in patients with good prognoses to determine if this treatment will be at least as effective as, but less toxic than, standard therapy. A total of 43 patients will be enrolled in order to obtain 36 patients that complete radiation treatment and have both biopsies taken. Thus, both the clinical primary endpoints and scientific secondary endpoints can be analyzed, as EGFR tumor information is useful for determining potential mechanisms of resistance to cetuximab. Based on the experience of UMCC 9921 and UMCC 2-21, accrual is expected to average one patient per month. To be considered evaluable, a patient must complete the full course of radiation/cetuximab. If radiation and/or cetuximab was stopped or modified due to toxicity, the patient is still evaluable. Inevaluable patients will be replaced.

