20.3 Analysis Plan

20.3.1 Primary Objectives

20.3.1.1 *To confirm that reducing treatment intensity in non-smoking patients with HPV-related oropharyngeal cancer does not significantly increase the proportion of patients whose tumors recur, compared to our previous experience in similar patients receiving standard-intensity chemo-RT.*

The primary index of recurrence will be the proportion of patients who have local recurrence, distant metastases or second primaries (secondary analyses will be performed on each of these endpoints individually) within two years of the end of treatment. In the primary analysis, *null* hypothesis that the proportion of patients who fail is *greater* than 0.20 will be tested using an exact binomial test (at significance level $\alpha=0.20$). The proportion of patients who recur will be calculated, with a 95% exact binomial confidence interval.

20.3.1.2 *To compare the toxicity in patients receiving reduced intensity treatment to similar patients treated with 7 weeks of chemotherapy concurrent with RT ("standard therapy") in UMCC 2-21.*

Dysphagia and mucositis are measured on continuous scales; there are both observer and patient reports. The null hypothesis of no difference in dysphagia and mucositis at three, twelve and twenty-four months posttreatment between the reduced-intensity therapy versus UMCC 2-21 will be tested ($\alpha=0.20$) in a repeated measures analysis of covariance. In addition, the statistical significance of the difference between the current trial and UMCC 2-21 in the proportions of patients experiencing clinically significant (NCI CTCAE Grade 3 or worse) toxicities will be assessed using Fisher's exact test

(a=0.20).

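### Patients who stop treatment for toxicity stay evaluable, but their 3-, 12- and 24-month toxicity measures, above all videofluoroscopy, may not be collected

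*Combined protocol and SAP*

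**What the plan says.** Four parts of the combined protocol and SAP bear on this.

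- **Follow-up after stopping.** Section 9.4 states: "Once patients discontinue treatment (Section 13.0) or have tumor progression/recurrence, they will be followed as clinically indicated for 3 years", counted from the end of radiation and/or cetuximab. The study calendar (Section 11.0) carries the same rule: "Note: Once patients discontinue treatment (Section 13.0) or have tumor progression/recurrence, they will be followed as clinically indicated for 3 years". There it stands under a table that includes the toxicity, questionnaire and videofluoroscopy rows.
- **Reasons for stopping.** Section 13.0 lists "Unacceptable adverse event(s), intercurrent illness which prevents further administration of treatment, patient preference, progressive disease" and also "life threatening or other unacceptable drug-related toxicity". It does not separate stopping cetuximab alone from stopping all treatment. Section 7.12 makes clear that the two can differ: "If toxicities prevent the administration of cetuximab, the subject may continue to receive radiation therapy".
- **Evaluability.** Section 20.1 states: "If radiation and/or cetuximab was stopped or modified due to toxicity, the patient is still evaluable".
- **Primary toxicity analysis.** Section 20.3.1.2 tests "The null hypothesis of no difference in dysphagia and mucositis at three, twelve and twenty-four months posttreatment" against UMCC 2-21, by repeated measures analysis of covariance at a significance level of 0.20. It gives no rule for missing values.

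**The concern.** The evaluability rule and the follow-up rule point in different directions for the same patients. A patient who stops for toxicity counts in the analysis set, yet a site could reasonably read 9.4 and the calendar note as releasing that patient from the fixed assessment schedule. The outcome data for a primary objective may then be absent for a reason connected with toxicity, in a trial that sets out to show less toxicity than a historical series. Outcomes that were never collected cannot be recovered at the analysis stage. The allowance of 43 enrolled for 36 does not cover this, because Section 20.1 ties it to completing radiation and having both biopsies.

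**Working it through.** **1. Is each measure protected after a stop?**

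| Measure | Text that might protect it | What that text covers |
|---|---|---|
| CTCAE items | 10.1 gathers them at follow-up visits for 3 years; 17.0 collects treatment-related late events for 3 years | Partial. Visit timing becomes discretionary if 9.4 governs the visits, and late-event reports are not the continuous scales tested in 20.3.1.2 |
| Questionnaires | 10.1 says the team will try to obtain certain information from all enrolled patients | Arguable. The sentence follows the employment and Performance Status items and may refer only to those |
| Videofluoroscopy | 10.2 times the studies from completion of RT | No explicit statement for patients who discontinue |

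Videofluoroscopy is the measure on which Section 20.4.3 bases its power statement.

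**2. Can the loss be related to outcome?** Yes, by at least one route. Mucositis is one of the two primary toxicity measures. Section 7.10 provides that cetuximab is discontinued if more than two dose reductions are needed for it. Such a stop happens during treatment, before the 3-month visit, so all three analysis time points could be lost.

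**3. The plan's own figure.** Section 20.4.3 claims at least 80% power for videofluoroscopy at a 58% decrease. It comes from a simulation whose control sample size and correlations are not given, so it cannot be strictly reproduced. A two-sample approximation uses 36 trial patients (20.1), 33 UMCC 2-21 patients (20.4.2.1; the number with videofluoroscopy is not stated), SD 1.18 and two-sided alpha 0.20:

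- Difference: 0.58 × (3.7 − 2.37) = 0.58 × 1.33 = 0.771.
- Standard error: 1.18 × √(1/33 + 1/36) = 0.284.
- Power: Φ(0.771/0.284 − 1.282) ≈ 0.92, consistent with the claim.

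**4. Hypothetical shift in the mean.** If a fraction f of patients is missing and their mean is δ worse than that of the patients observed, the observed mean is too low by f × δ. The documents give neither f nor δ. I assume f = 0.10 to 0.20, δ = 0.5 to 1 SD, and that every such patient is missing.

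- HNQOL eating domain (SD 18.9; rise 25.7 − 10.5 = 15.2):
  - low: 0.10 × 0.5 × 18.9 = 0.9, and 0.9/15.2 = 6%
  - high: 0.20 × 1 × 18.9 = 3.8, and 3.8/15.2 = 25%
- Videofluoroscopy (SD 1.18; rise 1.33):
  - low: 0.10 × 0.5 × 1.18 = 0.06, and 0.06/1.33 = 4%
  - high: 0.20 × 1 × 1.18 = 0.24, and 0.24/1.33 = 18%

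**5. Hypothetical effect on the test.** I simulated 20,000 trials of 36 against 33 with normal data, no true difference and a two-sided t-test at 0.20. Entries are the fall in mean videofluoroscopy score, then the chance of a false finding in favour of cetuximab-RT. With nothing missing that chance is 0.10.

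| Missing of 36 | Missing are exactly the worst swallowers | Missingness correlates 0.5 with dysphagia | Missing at random |
|---|---|---|---|
| 2 | 0.13; 0.22 | 0.07; 0.15 | none; 0.10 |
| 4 | 0.24; 0.35 | 0.12; 0.19 | none; 0.10 |
| 6 | 0.34; 0.49 | 0.17; 0.25 | none; 0.10 |
| 8 | 0.44; 0.62 | 0.22; 0.29 | none; 0.10 |

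Loss at random costs little power: with 8 missing, the approximation in step 3 falls from 0.92 to 0.90.

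**The case against.** The strongest reply is that the text permits this loss but does not require it. Section 9.4 sits under evaluation of response. Section 10, which governs toxicity and quality of life, makes no exception for patients who discontinue. Because 10.2 counts from completion of RT, a patient who stops cetuximab and finishes RT still has videofluoroscopy dates. Toxicity during treatment is recorded weekly, so the Grade 3 or worse comparison keeps the events that led to the stop. All of this stands, and it limits the point to what may happen. It does not remove the conflict, because the calendar note applies the rule to the whole schedule and 9.4 has little meaning except as a departure from that schedule.

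Two stronger readings are tempting.

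- **That the measures will go missing selectively in the patients with the worst dysphagia.** The documents do not support this. Rash and hypersensitivity also lead to stopping, and neither implies worse swallowing. Section 1.0 links dysphagia to the dose reaching the swallowing structures, so a patient who stops RT early might swallow better. The documents do not say how UMCC 2-21 followed patients who stopped; similar loss there would offset part of any bias. A repeated measures model could also recover something where some post-treatment visits exist.
- **That recurrences would be looked for less often in these patients.** The fixed examinations in 9.3 are themselves described as matching clinical practice, so nothing shows that follow-up under 9.4 would be materially sparser.

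**Conclusion.** The conflict between 20.1 on one side and 9.4 with the calendar note on the other is in the current text and touches a primary objective. Primary toxicity measures at 3, 12 and 24 months may go missing in evaluable patients, most clearly videofluoroscopy. The mucositis route makes outcome-related loss possible, and it could favour cetuximab-RT.

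Neither the size nor the direction of any bias is known. The figures above are sensitivity values that rest on an assumed stopping rate, an assumed deficit and complete loss in those who stop. Whether a cetuximab-only stop triggers 9.4 is also unclear, and that decides how many patients are affected. I rate this as something that should be fixed, with moderate confidence. In a preliminary trial it does not by itself invalidate the design.

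**What to change.** Change data collection only; no treatment rule needs to move. Reconcile 9.4, 10.1, 10.2, the calendar note, 13.0 and 20.1 as follows:

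1. State that stopping cetuximab and/or RT does not end protocol assessments.
2. State that the scheduled CTCAE, questionnaire and videofluoroscopy assessments at 3, 12 and 24 months are sought in all evaluable patients unless consent is withdrawn.
3. Say whether stopping cetuximab alone counts as discontinuation for the purposes of 9.4.
4. State how toxicity data after recurrence are handled, consistently with 17.2.4, which ends adverse event collection once another non-surgical therapy begins.
5. In 20.3.1.2, add a sensitivity analysis for missing toxicity outcomes. One option is to repeat the comparison with missing values set 0.5 and 1 SD worse than the model predicts. Report the number missing and the reason at each visit.

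The cost is a short amendment. The small downside is that some patients who stopped early will be asked to attend assessments that are already in the calendar.

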10.0 EVALUATION OF TOXICITY AND QUALITY OF LIFE

10.1 Validated quality of life questionnaires: HNQOL, UWQOL-HN, and XQ (Appendix B) will be given to patients before and periodically after radiation (1, 3, 6, 12, 18, 24 and 36 months, with a +/- 1 month window for each). Common Toxicity Criteria Adverse Events (CTCAE, v.4.0) observer related items will be gathered weekly during treatment and at every follow- up clinic visit through 3 years. As part of data collection related to the quality of life measures, pre and post-treatment employment status will also be recorded, as well as Performance Status Scale. Patients may be asked for this information during a clinic visit or contacted via phone. The study team will attempt to obtain this information from all enrolled patients.

10.2 Objective evaluation of swallowing will be made by videofluoroscopy and esophagogram. They will be performed in patients receiving definitive RT and chemotherapy. A baseline study will be performed either before RT starts or on one of the first five days of RT. Three follow-up studies will be done: one study at 3 to 4 months following RT completion (+/- 1 month), one study at 11 to 13 months following RT completion (+/- 1 month), and one study at 24 months following RT completion (with the acceptable window of 2 months prior or 6 months post). Each subject will be asked to swallow various food consistencies in varying amounts (5-15 mL). The consistencies included thin liquid barium (diluted with water) followed with non- diluted barium, followed with a puree, soft food (fruit mixed with barium) and a solid (shortbread cookie) coated with barium. The examinations will be recorded and analysis of the 3 phases of swallowing: oral, pharyngeal and esophageal will be made. Assessment will focus on bolus manipulation and control, bolus passage including cohesion, motility, and timing. The timing or duration of each swallowing phase will be determined. Also, the amount and incidence of aspiration and penetration, laryngeal sensation (response to penetrant/ aspirate) and residue/pooling after the swallow will be recorded. Laryngeal sensation will be determined to be good, reduced or poor. Reduced sensation would be consistent with a cough reflex that is delayed or intermittent. Poor sensation is defined when subjects elicit no spontaneous cough reflex or throat clear. These subjects are considered to be "silent" aspirators.

11.0 STUDY CALENDAR

Assessment	Pre-Treatment*	Day 0 Loading Dose	Day 7 (+/- 2 days)	Weekly during Treatment†	12-14 wks post RT (+/- 1 month)	Follow Up ³
H&P/Physician Evaluation	X			X	X	X
Smoking status and tumor HPV or p16 determination	X					
Biopsy	X		X ¹			
Buccal swab	X		X ¹			
COMP, Mg	X			X	X	
CBCP with diff	X			X	X	
PET-CT	X				X ²	
Dental Evaluation	X					
Toxicity Evaluation	X			X	X	X
QOL Questionnaire	X				X	X
Videofluoroscopy	X				X	X
Cetuximab		X		X		

* The pre-treatment period is prior to the administration of the cetuximab loading dose

† Radiation therapy will start within 4 days following Day 7 biopsy

¹Research biopsy will be performed 7 days (+/- 2 days) after cetuximab. This second biopsy will only be obtained if it can be done without general anesthesia.

²Restaging PET-CT will be obtained at 12-14 weeks.

³Follow Up: Examinations will be performed as comparable to clinical practice: at 1 month after the completion of therapy and then every 2 months during years 1 and 2, and at 3-month intervals during year 3. Toxicity evaluation will be collected at each visit. Quality of Life Questionnaires will be given to patients at follow-up visits 1, 3, 6, 12, 18, 24 and 36 months. Videofluoroscopy will be performed at 3, 12, and 24 months after therapy. Allowable windows for all these time points are +/- 1 month.

Note: Once patients discontinue treatment (Section 13.0) or have tumor progression/recurrence, they will be followed as clinically indicated for 3 years following the completion of radiation and/or cetuximab.

